# STUDY PROTOCOL

## Research Abstract

Over 100 million Americans suffer from high blood pressure and thus are at increased risk for cardiovascular disease and premature morality. Evidence supports the DASH (Dietary Approaches to Stop Hypertension) dietary pattern to reduce blood pressure. DASH is rich in fruits and vegetables, legumes, lean protein, and low-fat dairy, and reduced in red meats, sweets and processed foods. In the past 20 years, numerous trials have demonstrated the blood pressure-lowering effects of DASH across a diverse range of populations. As such, DASH is part of national dietary and blood pressure guidelines. Despite this strong evidence, fewer than 1% of U.S. adults with high blood pressure fully meet DASH guidelines. Like most efficacious interventions, the rate-limiting step involves dissemination. Behavioral trials testing DASH have been delivered primarily in-person, an approach that is effective but not accessible to the broader population. Innovative and accessible strategies to disseminate DASH, such as digital health, are critically needed. To address this need, we developed and tested the feasibility of a 3-month digital health intervention called DASH Cloud. The DASH Cloud intervention asked participants to track their diet daily using a commonly-used commercial tracking app with an extensive nutrient database. Our intervention technology platform extracted food and nutrient data from the app using an application programming interface (API). Each day, using this API software, we compared individual participant's nutrient intake to the recommended levels in the DASH diet. We then processed the data against an algorithm and sent automated text messages to each participant with information on DASH diet adherence and diet tips. Results indicated that we successfully recruited and retained individuals with elevated blood pressure, achieved high engagement with daily diet tracking and saw positive changes in diet quality. Based on the results of the feasibility trial, we will improve upon the personalization of the automated text messages and include a scalable and responsive way of delivering coaching, based on diet data received in the app. The efficacy of this approach will be tested via a fully-powered 12-month randomized controlled trial, Nourish. The trial will examine the effects of the intervention on changes in dietary quality and blood pressure among men and women with high blood pressure, using the new blood pressure guidelines for nonpharmacological treatment. The primary outcome is 6-month change in DASH adherence, as measured by 24-hour recalls. We will also measure DASH adherence at 12-months post-randomization. Secondary outcomes include changes in blood pressure and other physiological outcomes (e.g. weight, lipids, glucose). The scientific premise of this proposal represents establishing the efficacy of a previously deemed feasible approach for disseminating the DASH diet. With the millions of Americans in dire need of nonpharmacological treatments for blood pressure, the public health impact of disseminating the Nourish intervention could drastically reduce the incidence of cardiovascular disease. The findings from this study prepare us for a future implementation trial, testing the potential to implement DASH Cloud within clinics and other healthcare institutions, yielding

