
#### **Research Aims for main RCT:**

Aim 1: To determine the efficacy of the 6-month Nourish intervention, compared to an attention control arm, on 6-month changes in DASH adherence.

Aim 2: To determine the efficacy of the 6-month Nourish intervention, compared to an attention control arm, on 6-month changes in blood pressure. Exploratory aims: To explore the impact of the Nourish intervention, as compared to an attention control arm, on 6-month changes in relevant clinical, behavioral and psychosocial variables (i.e., engagement with intervention components, physical activity, medication use, self-efficacy, and intuitive eating, depression, etc).

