At the end of the interview, participants will be asked if they are interested in being contacted to participate in the main trial, Nourish, as another recruitment channel for the parent trial (and to help reach minority recruitment goals).

Nourish RCT: We will conduct a 2-arm randomized controlled trial (N=300) testing the efficacy of the 6-month DASH Cloud intervention, as compared to attention control, on 6- and 12- month changes in DASH adherence, blood pressure and other relevant outcomes. We will recruit participants using a multi-pronged strategy: 1) direct marketing; 2) local media; 3) social media; 4) community organizations; 5) primary care clinics and 6) Duke MyChart recruitment. Those that respond to initial study advertisements will be screened using an online screener to determine initial eligibility and complete an online informed consent process and complete some self-report measures (all in REDCap).

As we near the end of recruitment for our sample of 300 randomized participants, we plan to remove REDCap links on our study website that links to the REDCap project to ask participants to email the study email addressed to be sent the REDCap link, if enrollment is still open. This will ensure that we do not overenroll participants, as there is potentially a long period of time from screening to randomization and that participants are not unnecessarily screening, consenting and/or filling out surveys when the study already has enough people in the pipeline. Once recruitment is complete, the website and REDCap screener will be updated with a notice that recruitment for Nourish is complete.

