#### Follow-up Visits 3, 4, 5, 6 (Follow-up Months 2, 4, 6, 12)

- 2 weeks before each scheduled follow-up visit, ASA24 prompts are sent with reminders to be completed with reminders (as described above)
  - o If both ASA24s are not complete, can still do visit and prompt participant to complete the recall while in the visit:
    - Take BP
    - Ask ppt to log into ASA system with their information
    - Confirm medications and dosage
    - Administer surveys, if appropriate
    - Schedule next visit
  - O At end of visit, pay participant incentive (Amazon e-gift card):
    - \$20 for 2-month visit (Visit 3)
    - \$20 for 4-month visit (Visit 4)
    - \$40 for 6-month visit (Visit 5)
    - \$40 for 12-month visit (Visit 6)
- Automated reminders (REDCap emails)
  - O Appt needs to be confirmed with reminders for remote BP collection
- Send out online surveys for months 6 and 12 months to save time at appt:
  - o BP adherence med measures
  - o Physical activity
  - o Self-efficacy for healthy eating
  - Psychosocial measures (sleep, depression, stress, intuitive eating, etc)
  - O Personalization survey (months 2 and 4 only as intervention ends at month 6) for Ix arm only
- 6-month visit protocol will include reminders about not receiving any more feedback and satisfaction (see 6-month protocol)
- 9-month retention protocol (see 9-month protocol)
- 12-month visit protocol will include closing out participation in the study:
  - O Thank them for participating over the last year.
  - O Share free dietary tracking app resources (Nourish app is turned off)- e.g. Nutritionix, My Fitness Pal, that have nutritional data, etc.

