## Statistical analysis plan

Demographic and baseline data will be examined for integrity of randomization scheme and the homogeneity of study arms. If any demographic and baseline data are not balanced between the two study arms and are believed to affect the outcome, we will consider adjusting these variables in the modeling process. All analyses will be based on intention-to-treat (ITT) principles.

We will assess the overall intervention effect on change of DASH score from baseline to 6 months by a two-sample t-test. To understand how DASH score improves over time from baseline to 6 months, and sustains through 12-month follow-up between study arms, we will plot observed DASH score vs. time (baseline, 2-month, 4- month, 6-month, 12-month) by two study arms. Linear mixed models will be built to test the primary hypotheses. If we observe a linear trend in the previous plot, our model will contain fixed effects including a group variable (intervention vs. control), time, and intervention by time interaction. To account for the correlations within the same participant over time, we will include a random intercept and random slope for time in the model. If there is a quadratic trend in time, we will also include a quadratic term for time in the model. To account for the stratified block randomization design, our models will also include our randomization stratification variables, blood pressure risk category and blood pressure medication status. If any other demographic or baseline variables are statistically different between the two study arms, then these variables will be included in a stepwise model selection process for the linear mixed model. We will evaluate the primary hypotheses by testing the null hypothesis that the time by intervention parameter is 0. Similar analysis will be conducted for changes in blood pressure and relevant clinical, behavioral and psychosocial variables. If the distribution of any of the outcomes is heavily skewed, then we will either appropriately transform the data so it's normally distributed or use a generalized linear mixed model with an appropriate link function.

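### The SAP's only modelled route to a 12-month effect is one time-by-arm slope, which cannot represent an effect that is kept or lost after the intervention ends at month 6

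*Combined protocol and SAP*

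**What the plan says.** The Nourish RCT paragraph under Design & Procedures describes a trial "testing the efficacy of the 6-month DASH Cloud intervention, as compared to attention control, on 6- and 12- month changes in DASH adherence", and extends this to blood pressure and other outcomes. The Research Aims are narrower: Aim 1 compares the intervention, "compared to an attention control arm, on 6-month changes in DASH adherence". The Research Abstract makes 6-month change primary and adds only: "We will also measure DASH adherence at 12-months post-randomization".

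The SAP names three analyses:

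- a two-sample t-test of change in DASH score from baseline to 6 months;
- a plot by arm at baseline, 2, 4, 6 and 12 months, introduced with the aim of seeing how the score improves "and sustains through 12-month follow-up between study arms, we will plot observed DASH score vs. time";
- a linear mixed model with arm, time and their interaction, a random intercept and slope, and a quadratic term for time if a quadratic trend is seen. The hypothesis is evaluated by "testing the null hypothesis that the time by intervention parameter is 0".

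Blood pressure and the other outcomes get a similar analysis. Neither the SAP nor the protocol's Data Analysis section names a 12-month contrast, a 12-minus-6-month contrast, a change of slope at month 6, or visit as a category. The follow-up visit section gives the personalization survey at "months 2 and 4 only as intervention ends at month 6".

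**The concern.** Months 6 to 12 are off-intervention follow-up. The natural question is whether the arm difference present at month 6 is kept, partly lost or wholly lost by month 12, so a bend at month 6 is to be expected. A single interaction slope has no room for a bend. The plot shows observed means but yields no estimate or interval and does not deal with missing data.

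Both arms supply dietary recalls and blood pressure at 12 months. If the plan is followed as written, a statement about 12-month efficacy or maintenance would rest on a slope whose accuracy depends on how the effect built up, or on a contrast chosen after the data were seen.

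**Working it through.** **Inputs from the documents.** Visits at 0, 2, 4, 6 and 12 months (SAP, analysis section). A 6-month difference of 1 unit, SD of change 2, alpha .01, 90% power, 242 participants, and 300 after 20% attrition (SAP, opening paragraph). Allocation 1:1 (Design & Procedures).

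**Assumptions.** The path of the arm difference before month 6, its value at month 12, complete balanced data, two-sided tests, and the SD of 12-month change.

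**1. The plan's own figure.** Per arm, n = 2 x (2.576 + 1.282)^2 x (2/1)^2 = 119.0, so 120. The t-based calculation gives 120.7, so 121 per arm and 242 in total, as stated. 242/0.8 = 302.5, close to the stated 300. The sample size is not in dispute. It concerns month 6; the documents give no power for month 12.

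**2. What the model can represent.** Write the modelled arm difference as D(t) = a + b t. The difference in change from baseline is then b t: 6b at month 6 and 12b at month 12, always in the ratio 1 to 2. A quadratic time term shared by both arms cancels from the difference, so it does not alter this.

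**3. Expected slope.** With complete balanced data and a random intercept and slope, generalised least squares for b equals ordinary least squares. The mean visit time is 4.8, and the sum of squares is 23.04 + 7.84 + 0.64 + 1.44 + 51.84 = 84.8. Hence b = sum of (t - 4.8) D(t) / 84.8. Let D12 be the true difference at month 12.

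- Path A, linear rise (0, 1/3, 2/3, 1, D12): 12b = 12 x (-0.267 + 7.2 D12)/84.8 = -0.038 + 1.019 D12.
- Path B, 1 unit reached by month 2 and held to month 6 (0, 1, 1, 1, D12): 12b = 12 x (-2.4 + 7.2 D12)/84.8 = -0.340 + 1.019 D12.

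| True D12 | 12b, path A | 12b, path B | 6b, path A | 6b, path B |
|---|---|---|---|---|
| 0 (lost) | -0.04 | -0.34 | -0.02 | -0.17 |
| 0.5 (half kept) | 0.47 | 0.17 | 0.24 | 0.08 |
| 1 (kept) | 0.98 | 0.68 | 0.49 | 0.34 |

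The true month-6 difference is 1 in every row. On path B the 12-month change is understated by about a third of a unit throughout. A fully lost effect appears as a reversal, and a fully kept effect appears as one-third lost.

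The slope alone also cannot tell two quite different histories apart. Path A fully kept gives b = 0.082 per month. No effect until 1 unit appears at month 12 gives b = 7.2/84.8 = 0.085.

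**4. The direct contrast.** A 12-month difference in change with visit as a category makes no assumption about shape. With 300 x 0.8 = 240 analysed, 120 per arm, and SD 2 carried over to month 12, its standard error is 2 x sqrt(2/120) = 0.26. Power at two-sided alpha .01 is 90% for 1 unit, 63% for 0.75 and 26% for 0.5. With SD 2.5 it is 70%, 40% and 15%.

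**The case against.** **The formal aims are 6-month only.** This stands. Twelve-month efficacy appears in the design description, not in the Research Aims, and the power calculation addresses month 6. A reader might infer that a formal aim is left unanswered; the documents do not support that. But the design description does state 12-month efficacy, and the SAP does set out to show whether the score is sustained.

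**The quadratic term may deal with the bend.** The linear model is conditional on a linear trend in the plot, and a rise followed by a loss is not linear. But the added term is written for time only, and as written it leaves the arm difference linear. If it were crossed with arm, path A would give differences in change at months 6 and 12 of 0.97 and 1.05 (kept) or 0.94 and 0.10 (lost). That would largely cure the problem on that path. The SAP would then have two interaction parameters, whereas it names one to test.

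**The 6-month t-test, read with 12 x slope, separates kept from lost.** On path A it does, and the slope is then nearly right for month 12. On path B it does not: 1 unit at month 6 followed by -0.34, 0.17 or 0.68 would misstate what was kept.

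**A stronger reading to avoid.** A reader might take the fitted arm difference in level at month 12 (intercept plus 12 x slope) as showing a false benefit. On path A with the effect lost it is 0.415 - 0.038 = 0.38 against a truth of 0. That sum includes a spurious fitted baseline gap of 0.415. The plan concerns change from baseline, for which the same fit gives -0.04, so the level figure does not support the criticism.

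**Conclusion.** The point holds as a gap in the 12-month analysis. The structural part needs no assumption about the data: with one interaction slope and a shared quadratic term, the modelled difference in change at month 12 is always twice that at month 6.

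The size of the error does depend on the path. It is 0.04 unit or less if the effect builds linearly to month 6, and 0.32 to 0.34 unit if it is reached by month 2 and held. The second is about a third of the 1-unit effect the trial is planned on. The documents do not say which path to expect, and the calculations assume complete data.

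A reader might infer that the trial can yield no valid 12-month estimate, or that the sample size or the 6-month t-test is undermined. None of this follows. The slope can be close to the truth, the data for a direct contrast are already being collected, and the 6-month t-test does not use the slope. The matter should be settled in the SAP before analysis, as a secondary issue.

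**What to change.** In the analysis section of the SAP:

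- Fit visit (0, 2, 4, 6 and 12 months) as a categorical factor crossed with arm in the planned mixed model, for DASH score, systolic and diastolic blood pressure.
- Prespecify two secondary estimates for each, with confidence intervals: the between-arm difference in change from baseline to 12 months, and the 12-minus-6-month difference between arms.
- State that any claim about maintenance rests on these estimates, and not on the plot or the slope. Given the limited power for a partly kept effect, the interval matters more than the test.
- Align the description of the 12-month objective in Design & Procedures with the Research Aims, labelling it as secondary.

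The cost is SAP wording, a few more model parameters and some added secondary estimates. No new data are needed, and the alpha for the primary 6-month comparison is unchanged.

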#### **RCT**:

Power and sample size. Using data from the pilot study we anticipate systolic blood pressure changes in intervention vs control as follows: -3.4 (SD=8.6) mmHg and 2 (SD=9.3) mmHg which results in an effect size of 0.6. The effect size for diastolic blood pressure is 0.75 based on changes in intervention vs control of -3.8 (SD=7.9) mmHg vs. 1.6 (SD=6.4) mmHg. With 90% power and a type I error rate (alpha) of .01, we can detect the expected effect size with the proposed sample size of 300.

Demographic and baseline data will be examined for integrity of randomization scheme and the homogeneity of study arms. If any demographic and baseline data are not balanced between the two study arms and are believed to affect the outcome, we will consider adjusting these variables in the modeling process. All analyses will be based on intention-to-treat (ITT) principles.

Aim 1: To understand how DASH score improves over time from baseline to 6 months and sustains through 12-month follow-up between study arms, we will plot observed DASH score vs. time (baseline, 1- month, 2-month, 4-month, 6-month, 12-month) by two study arms. Linear mixed models will be built to test the primary hypotheses. If we observe a linear trend in the previous plot, our model will contain fixed effects including group variable (intervention vs. control), time, and intervention by time interaction. To account for the correlations within the same participant over time, we include a random intercept and random slope for time in the model. If there is a quadratic trend in time, we will also include a quadratic term in time in the model. If any of the demographic or baseline variables are statistically different between the two study arms, then these variables will be included in a step-wise model selection process for the linear mixed model. We will estimate model parameters using the SAS/STAT procedure MIXED (SAS Version 9, Cary, NC). We will evaluate the primary hypotheses by testing the null hypothesis that the time by intervention parameter is 0.

Aims 2 and 3: Similar analysis will be conducted for changes in blood pressure (Aim 2) and relevant clinical, behavioral and psychosocial variables (Aim 3). If the distribution of any of the outcomes is heavily skewed, then we will either appropriately transform the data so it's normally distributed or use a generalized linear mixed model with an appropriate link function.

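### Beyond the two stratification factors, covariates for the primary mixed model are picked by baseline significance tests and a stepwise step; naming them in advance, with time terms, is a cheap improvement

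*Combined protocol and SAP*

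**What the plan says.** The SAP (Statistical analysis plan) fixes two covariates: "our models will also include our randomization stratification variables, blood pressure risk category and blood pressure medication status". For everything else it gives a trigger, "If any other demographic or baseline variables are statistically different between the two study arms", and a consequence, "these variables will be included in a stepwise model selection process for the linear mixed model". It gives no candidate list, no level for the baseline tests, no criterion for entering or staying, and no form of entry (main effect, or main effect plus interaction with time).

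The same section opens with another rule: "If any demographic and baseline data are not balanced between the two study arms and are believed to affect the outcome, we will consider adjusting". Nothing says how the two rules relate.

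The tested quantity is the interaction: "We will evaluate the primary hypotheses by testing the null hypothesis that the time by intervention parameter is 0". Baseline DASH score is one of the response time points, not a covariate: "we will plot observed DASH score vs. time (baseline, 2-month, 4- month, 6-month, 12-month) by two study arms". The SAP also specifies a two-sample t-test on 6-month change in DASH score, without covariates.

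The protocol (Data Analysis & Statistical Considerations, RCT, Aim 1) describes the same model with the same trigger, "If any of the demographic or baseline variables are statistically different between the two study arms", and the same step, "these variables will be included in a step-wise model selection process for the linear mixed model". It also carries the discretionary rule, but it does not put the stratification factors in the model. Both documents extend the approach to blood pressure and the other outcomes.

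**The concern.** After randomisation, baseline differences between arms are chance. A significance test therefore picks candidates by how unbalanced they happen to be, not by how well they predict outcome. The stepwise step then screens on outcome, but only among those candidates. A balanced prognostic variable is never considered.

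The protocol itself supplies an example. Under Design & Procedures it describes blood pressure risk category as important for the intervention effect on blood pressure, and says that stratification equalises it between arms. Under the protocol's own selection rule it would normally stay out of the blood pressure model.

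The rule also misses its target. The tested parameter is a difference in time trend. A covariate entered only as a main effect shifts levels, not trends, so it does not correct an imbalance in that contrast. If the covariate enters with time instead, the estimate depends on a selection made from data by arm. What is at stake is pre-specification of the model for the primary hypotheses, and some unused precision.

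**Working it through.** **1. The plan's own sample size.** Inputs from the SAP: difference 1, SD 2, alpha .01, power 90%. Taking alpha as two-sided, n per arm = 2(2.576 + 1.282)² × 2²/1² = 119.1, so 120 per arm and 240 in total. The t-test version needs 120.7, so 121 per arm and 242 in total, which matches the SAP. Also 242/0.8 = 302.5, against 300 stated. The sample size is not in question.

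**2. How often the trigger fires by chance.** The Nourish measures/constructs table lists about 35 baseline rows besides dietary recall, blood pressure and blood pressure medication. This is an upper bound, because rows overlap. The test level is not stated, so 5% and 1% are assumptions. P(at least one) = 1 − (1 − a)^k:

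| k | a = .05 | a = .01 |
|---|---|---|
| 10 | 40% | 10% |
| 20 | 64% | 18% |
| 35 | 83% | 30% |

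These figures assume independent tests. At 5% with correlation 0.3 or 0.5 between test statistics they fall to 54% or 42% (k = 20) and 71% or 54% (k = 35).

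**3. Model used for the remaining checks.** N = 300; visits at 0, 2, 4, 6 and 12 months; random intercept and slope; maximum likelihood, as in the SAP. Assumed slope variance 2 per (6 months)² and residual variance 1. The variance of 6-month change is then 2 + 1 + 1 = 4, so its SD is 2, as in the SAP. Covariate strength R² is the share of variance of participants' fitted slopes that the covariate explains. The documents give no value; .05, .10 and .20 are assumed. They correspond to 3%, 6% and 12% of the variance of 6-month change.

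**4. Effect of entering one covariate that has triggered** (baseline imbalance forced to |z| > 1.96; 300 replicates per setting). Median shift in the time-by-intervention estimate, in SE:

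| Entry | Data | R² .05 | .10 | .20 |
|---|---|---|---|---|
| Main effect | complete | 0.000 | 0.000 | 0.000 |
| Main effect | 20% random dropout | 0.023 | 0.030 | 0.047 |
| With time | complete | 0.53 | 0.72 | 1.02 |
| With time | 20% random dropout | 0.46 | 0.67 | 0.98 |

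For main-effect entry under dropout, including R² = 0 and dropout that depends on observed change, medians run from 0.01 to 0.05 SE and 99th percentiles from 0.05 to 0.19 SE. The SE ratio is 1.00.

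**5. The whole procedure, on the time-entry reading.** Trigger at 5%, then backward elimination at an assumed p < .05; complete data; 8,000 null replicates per cell. Percentage of trials in which any covariate is retained (R² .05/.10/.20):

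| Candidates | 1 prognostic | 4 prognostic |
|---|---|---|
| 10 | 6.6/7.1/7.4 | 10.2/15.9/18.7 |
| 20 | 9.2/9.0/9.0 | 13.2/17.6/21.6 |
| 35 | 12.7/13.4/12.8 | 16.0/20.5/24.3 |

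The unconditional median shift is therefore 0. A shift above 0.5 SE occurs in 0.9 to 10.0% of trials. Rejection under the null at .01 is 0.7 to 1.2%, against 0.7 to 1.3% unadjusted.

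**6. Gain from naming covariates with time terms.** SE ratio = √(1 − R²) = 0.975, 0.949 and 0.894 for R² .05, .10 and .20. Maximum likelihood fits gave 0.978, 0.950 and 0.896 with complete data, and 0.977, 0.952 and 0.905 with 20% dropout. Main effects alone give no gain. If three time terms are unrelated to change, the cost is √(1/(1 − 3/299)) = 1.005.

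**7. A second simulation, on 6-month change** (240 evaluable, 35 candidates of which 3 prognostic). Here strength is the share of change variance explained, assumed .10, .20 or .30. Power at a 1-unit difference:

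| Analysis | .10 | .20 | .30 |
|---|---|---|---|
| Unadjusted | 89.6% | 90.0% | 89.9% |
| Trigger plus stepwise, with time terms | 89.9% | 90.7% | 90.7% |
| Named in advance, with time terms | 92.5% | 95.5% | 97.7% |

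Type I error under the stepwise rule was 0.0107, 0.0097 and 0.0078 against a nominal 0.01.

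**The case against.** The best reply is that little follows from this. On the natural main-effects reading the tested contrast hardly moves. The large shifts need time entry, which the plan never mentions, together with a covariate already known to be unbalanced and an R² that no document supports. The t-test on 6-month change, which reproduces the stated 242, uses no covariates. All of this stands, and it is why the point is an improvement and not an error.

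Three further points are partly right:
- The risk-category example works only for the protocol section read alone, because the SAP puts the stratification factors in. It also concerns blood pressure, not DASH change, and the documents identify no omitted prognostic variable for DASH.
- The SAP can be read as elaborating the protocol, and its discretionary rule does mention prognosis. That rule still needs imbalance first, is optional, and is not ranked against the other.
- The linear or quadratic time form is chosen from the plotted data, so fixing covariates does not remove every data-dependent choice. That is a separate issue.

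None of this supplies a reason to keep the significance trigger or the stepwise step.

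**Conclusion.** The point holds as a cheap improvement. The documents state an inferior selection method for the primary model, give two different fixed covariate sets, and leave two adjustment rules unreconciled. There is no type I inflation and no shortfall from the stated power. As written, the adjustment is close to inert if covariates enter as main effects. If they enter with time, the result depends on a selection made after data by arm are seen. The size of any precision gain rests wholly on the assumed R² and is nil if the named covariates do not predict change. The conclusions on pre-specification and on main-effect entry do not need a particular R².

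**What to change.** In both the SAP and the protocol's Aim 1 analysis text:
- Delete the baseline significance tests, both imbalance-triggered rules and the stepwise step, and use identical wording in the two places.
- Before data by arm are seen, fix one covariate set: the two stratification factors plus any few named prognostic variables already collected.
- State that each covariate enters with its time interaction, in the same time form as the model.
- Keep baseline DASH score as the first response time point.
- Report baseline tables descriptively, and label any other adjustment as a sensitivity analysis.

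The cost is a wording edit and a few model terms, with no new data. With the three blood pressure categories listed under Design & Procedures and medication yes/no, the stratification factors need 2 + 1 = 3 linear time terms (6 if time is quadratic). Each further covariate with one parameter adds one (two if quadratic). That category list has evident gaps, so its levels must be settled before the count is final. What is given up is the freedom to choose covariates afterwards.
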